#### 6.2.1.2. Objective Response Rate

Objective response rate is defined as the proportion of subjects with best overall response during andecaliximab therapy of complete response (CR) or partial response (PR) based on RECIST 1.1. Subjects, who do not have sufficient baseline or on-study tumor status information to be adequately assessed for response status (ie, those with best overall response of NE or no disease [ND]) or received anticancer therapy other than the study treatment prior to achieving CR or PR, will be considered as non-responders and will be included in the denominators in calculations of response rates.

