5.3.1.1. GS-5745/Placebo (Study Drug)

If a subject experiences a Grade 3 or greater toxicity considered secondary to study drug (GS-5745/placebo), treatment will be postponed until the toxicity returns to Grade 0-1 (as defined by NCI CTCAE v 4.03) or returns to the subject's baseline value. If the toxicity returns to Grade 0-1 or the subject's baseline value, the subject may resume GS-5745 at the originally assigned dose level.

If the event does not resolve to Grade 0-1 or the subject's baseline within 28 days, treatment with study drug (GS-5745/placebo) must be permanently discontinued. If the subject experiences a recurrence of the Grade 3 or greater toxicity after restarting study drug, treatment with GS-5745/placebo will be discontinued. Subjects who permanently discontinue treatment with study drug (GS-5745/placebo) may continue treatment with mFOLFOX6 after consultation with the medical monitor.

Subjects who are not receiving any chemotherapy (mFOLFOX6) should not receive study drug (GS-5745/placebo) as monotherapy. Investigators should contact the Gilead Medical Monitor with any questions regarding study drug dose modification, interruption or discontinuation.

5.3.1.2. mFOLFOX6

Recommended dose reduction for the components of mFOLFOX6 is described in [Table 5-1](#) and is based on the adverse event (AE) table described in [Appendix 5](#). Sites may also follow their institutional practice for dose reductions. Leucovorin doses may be adjusted per institutional guidelines in the event of a supply shortage.

Subjects who interrupt all components of mFOLFOX6 for greater than 28 days secondary to drug toxicity(s) that do not resolve should permanently discontinue all study treatment.

Subjects who permanently discontinue all components of mFOLFOX6 should also discontinue GS-5745/placebo.

Investigators should contact the Gilead Medical Monitor with any questions regarding study drug dose modification, interruption or discontinuation.

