### 6.2.9. Disease and Response Assessment

#### 6.2.9.1. Tumor Imaging

Either contrast-enhanced CT or gadolinium-enhanced MRI of the chest, abdomen, and pelvis will be performed at screening, every 8 weeks during the study (starting from Cycle 1 Day 1) and at the EOS visit if one has not been performed within the last 8 weeks. Tumor burden will be evaluated solely based on radiographic imaging per RECIST v 1.1. Chest x-ray, ultrasound, endoscopy, laparoscopy, positron-emission tomography, radionuclide scans, or tumor markers will not be considered for response assessment.

For radiographic evaluations, the same method of assessment and the same technique (eg, scan type, scanner, subject position, dose of contrast, injection/scan interval) should be used to characterize each identified and reported lesion at baseline and during study treatment and follow-up.

Scans taken as part of standard medical practice up to 42 days prior to randomization can be used for Screening as long as they meet all study requirements. During the treatment phase, scans may be performed at time points other than every 8 weeks as clinically indicated to assess tumor progression.

For subjects who stop study treatment in the absence of disease progression (eg, experienced unexpected toxicity), scans should continue to be collected approximately every 8 weeks until disease progression or initiation of systemic anti-tumor therapy other than the study treatment, whichever is earlier.

All relevant clinical and radiographic information required to make each assessment must be made available for source verification and submission to a central reader. Scans will be transferred to a central reader for collection and future analysis. Disease progression will be determined by the investigator or qualified designee.

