##### **3.1.3. Safety Analysis Set**

The Safety Analysis Set includes all subjects who received at least 1 dose of andecaliximab/placebo. This is the primary analysis set for safety analyses.

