### 6.2.2.2. Objective Response Rate

Another secondary efficacy hypothesis to be tested is that there is no difference between Treatment Group (Group T) and Control Group (Group C) in ORR. Using  $R_T$  and  $R_C$  to denote the objective response rate of Treatment Group (Group T) and Control Group (Group C), respectively, the statistical hypotheses to be tested in this study will be:

$$H_0: R_T = R_C$$

$$H_1: R_T > R_C \text{ (Group T is superior to Group C in terms of ORR)}$$

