### 6.2.3.2. Objective Response Rate

The ORR will be compared between the 2 treatment arms using the Cochran-Mantel-Haenszel test adjusted for the stratification factors based on the ITT analysis set. ORR and the corresponding 95% CI based on Clopper-Pearson method of each treatment arm will be presented. The odds ratio comparing the 2 treatment arms adjusted for the stratification factors will be presented along with 95% CI. The 2-sided 95% CI of difference for ORR between the treatment and placebo will be calculated based on stratum-adjusted CMH proportion {Koch 1989}.

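### SAP 6.2.1.2 ends the ORR response window when study drug stops, so a first response on continuing mFOLFOX6 would not count

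*SAP*

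**What the plan says.** - **ORR definition.** SAP 6.2.1.2 takes "the proportion of subjects with best overall response during andecaliximab therapy of complete response (CR) or partial response (PR"). Its second sentence makes non-responders of subjects without adequate baseline or on-study tumor information, and of those who "received anticancer therapy other than the study treatment prior to achieving CR or PR".
- **Both arms are compared.** SAP 6.2.2.2 states the hypotheses in terms of the "objective response rate of Treatment Group (Group T) and Control Group (Group C"). SAP 6.2.3.2 says "The ORR will be compared between the 2 treatment arms using the Cochran-Mantel-Haenszel test". Elsewhere the SAP names both arms when it refers to study drug. The Safety Analysis Set in SAP 3.1.3, for example, is "all subjects who received at least 1 dose of andecaliximab/placebo".
- **Visible protocol definitions.** The synopsis and Protocol 2.5 define ORR as the proportion achieving CR or PR, the latter by RECIST v1.1. Neither gives a time window.
- **Study drug can stop before chemotherapy.** Protocol 5.3.1.1: "Subjects who permanently discontinue treatment with study drug (GS-5745/placebo) may continue treatment with mFOLFOX6 after consultation with the medical monitor".
- **Scans continue.** Protocol 6.2.9.1 schedules imaging "every 8 weeks during the study (starting from Cycle 1 Day 1"), and footnote p of Protocol Appendix 2 makes the schedule independent of cycle number and dose interruption. After treatment stops without progression, "scans should continue to be collected approximately every 8 weeks until disease progression or initiation of systemic anti-tumor therapy other than the study treatment".
- **RECIST default.** Protocol Appendix 7, section 4.4, runs best overall response from the start to the end of study treatment, and asks protocols to say whether later assessments count.
- **Meaning of study treatment.** SAP 7.1.5.1 uses the term for andecaliximab/placebo together with chemotherapy.

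**The concern.** The wording has two faults. The literal one is that placebo subjects receive no andecaliximab, so none of their responses could qualify. The one that matters survives inserting the missing word: the window then closes at study-drug discontinuation, which can come before the end of chemotherapy and before the end of tumor assessment.

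ORR is the second alpha-controlled secondary endpoint, tested at one-sided 0.016 only if OS and then PFS succeed. Study-drug discontinuation happens after randomization and can follow toxicity attributed to study drug, so equal losses in the two arms cannot be taken for granted. A programmer would also have to choose between readings that can classify the same subject differently. That choice should be settled in writing before unblinding.

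**Working it through.** The plan gives no power, sample size or expected rate for ORR, so it has no figure to reproduce. The main check is a comparison of texts.

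**1. Can the two windows differ?** Under Protocol 5.3.1.1 and 5.3.1.2, a subject who permanently stops all mFOLFOX6 should also stop study drug, but the reverse need not hold. A window ending with study drug is therefore never longer than one ending with all study treatment. It is shorter exactly when study drug stops first.

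**2. Which responses are classified differently?**

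| When CR/PR is first seen | Visible protocol definition with RECIST default | SAP 6.2.1.2, read as andecaliximab/placebo |
|---|---|---|
| On study drug | Counts | Counts |
| Study drug stopped, mFOLFOX6 continuing | Counts | Does not count |
| All study treatment stopped, no new therapy | RECIST default excludes; protocol asked to say | Does not count |
| After non-study anticancer therapy | RECIST asks protocol to say | Non-responder |

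Only the second row is a clear conflict.

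**3. Fit within the SAP paragraph.** The second sentence speaks of on-study tumor information and sets a cut-off at new anticancer therapy. Protocol 3.4 makes starting such therapy without progression a reason to discontinue study treatment. If the window had already closed when study drug stopped, the new-therapy rule would have little left to do. The two rules can be applied together, but they point to different end dates.

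**4. Timing.** Doses fall on days 1, 15, 29 and 43. The first scheduled scan is at 8 weeks, day 57, with a ±7-day allowance in Protocol Appendix 2, so day 57 − 7 = day 50 at the earliest. The SAP does not say when therapy ends. For a last dose on day 29, even a full 14-day dosing interval runs only to day 42. A subject who stops study drug by then and stays on mFOLFOX6 has no scheduled scan inside the window.

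**5. Illustration of size.** Two inputs are assumed, because the documents give neither:
- s, the share per arm that stops study drug before a first response and stays on mFOLFOX6: 1–5%.
- r, the share of those who respond later: 20–40%.

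Uncounted responders per arm = 215 × s × r:
- 215 × 0.01 × 0.20 = 0.43 (0.2 ORR points)
- 215 × 0.05 × 0.40 = 4.30 (2.0 ORR points)

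Equal losses in percentage points leave the ORR difference unchanged. To scale an imbalance, take SE = √(2p(1−p)/215) and the one-sided 0.016 critical value 2.144. Here 0.40 is the historical rate in Protocol 1.4, 0.49 is the midpoint of its 40% and 58%, and 0.30 is assumed.

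| p | SE (points) | Difference needed (points) | z-shift per 1-point imbalance |
|---|---|---|---|
| 0.30 | 4.42 | 9.48 | 0.226 |
| 0.40 | 4.72 | 10.13 | 0.212 |
| 0.49 | 4.82 | 10.34 | 0.207 |

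Each point of imbalance is thus about 10–11% of the difference needed. This scaling holds for any ORR misclassification. It does not show that this wording causes an imbalance.

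**The case against.** **It is loose drafting, not a rule.** The SAP gives no end date for therapy here, although it states explicit day counts where it wants a window tied to study drug (SAP 7.1.5.1 and 7.2.2.1). Stopping study drug is not in the second sentence's list of reasons for non-response. The intent may well be the broader window, but the phrase still stands in the definition of a formally tested endpoint and its plain sense is restrictive. This argues for rewording it.

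**A treatment-based window is already in the protocol.** Protocol 2.5 defers to RECIST v1.1, whose appended text runs to the end of treatment. This stands for responses first seen after all treatment has stopped. It does not cover a window that closes while mFOLFOX6 continues.

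**The group is narrow.** The route in Protocol 5.3.1.1 requires Grade 3 or greater toxicity attributed to study drug that fails to resolve within 28 days or recurs. Subjects with only non-measurable disease are eligible and cannot have a PR under the appended RECIST Table 2, which lowers any late response rate. Both points stand and support a small effect.

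**Some text cannot be seen.** Protocol 8.5.2 and part of the synopsis methods are redacted, and the sensitivity list under SAP 6.2.4 is not visible. SAP 2.4 lists only the PD-L1 subgroups as a change, but a reader who infers an undeclared departure from the protocol goes further than the visible text allows.

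**Conclusion.** The point holds as a minor one. As worded, the SAP leaves out a first CR or PR that occurs after study drug stops while mFOLFOX6 continues. The visible protocol definitions and the RECIST default would both count that response.

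Three stronger inferences are not supported:
- *That the control arm would be scored with no responders.* The hypotheses and the test in SAP 6.2.2.2 and 6.2.3.2 need a rate in each arm, and the SAP's usual term covers both.
- *That every response on a post-discontinuation scan is wrongly dropped.* Once all study treatment has stopped, RECIST excludes such responses by default and leaves the choice to the protocol. That question is open.
- *That the ORR test is biased in a known direction.* With a true ORR of 40% in both arms, if only the control arm lost 5% of its responses, the one-sided rejection probability would rise from 0.016 to 0.043. If only the treatment arm did, it would fall to 0.005. Nothing in the documents says which arm, if either, loses more.

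The size cannot be derived from the documents. The 0.4 to 4.3 uncounted responders per arm rest wholly on the assumed 1–5% and 20–40%. OS, PFS and the ITT denominator for ORR are not affected.

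**What to change.** Replace the phrase in SAP 6.2.1.2 with: *best overall response of CR or PR from randomization until the earlier of disease progression or the start of non-study anticancer therapy, in both arms, regardless of discontinuation of andecaliximab/placebo.* This joins the SAP's own new-therapy rule to the scan end points in Protocol 6.2.9.1. The progression limit comes from the latter, since the SAP paragraph does not contain one. The wording also settles the open question by counting responses seen after all treatment stops and before either end point.

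If an on-treatment window is intended, end it at discontinuation of all study treatment (andecaliximab/placebo and chemotherapy), define that date, and word it identically for both arms. List it in SAP 2.4 unless the redacted Protocol 8.5.2 already contains it. Merely inserting placebo into the present phrase would not be enough, because the RECIST default does not support a window that closes while chemotherapy continues. Check also whether the list under SAP 6.2.4 already includes an alternative window.

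The cost is one sentence and the matching derivation, made before unblinding. No new data are needed, because the scans are already scheduled.

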## 6.2.2. Statistical Hypothesis for the Secondary Efficacy Endpoints

### 6.2.2.1. Progression-free survival

The secondary efficacy hypothesis to be tested is that there is no difference between Treatment Group (Group T) and Control Group (Group C) in PFS. Using  $F_T(t)$  and  $F_C(t)$  to denote the progression-free survival distribution functions of Treatment Group (Group T) and Control Group (Group C), respectively, the statistical hypotheses to be tested in this study will be:

$$H_0: F_T(t) = F_C(t)$$

$$H_1: F_T(t) > F_C(t) \text{ (Group T is superior to Group C in terms of PFS)}$$

### 6.2.2.2. Objective Response Rate

Another secondary efficacy hypothesis to be tested is that there is no difference between Treatment Group (Group T) and Control Group (Group C) in ORR. Using  $R_T$  and  $R_C$  to denote the objective response rate of Treatment Group (Group T) and Control Group (Group C), respectively, the statistical hypotheses to be tested in this study will be:

$$H_0: R_T = R_C$$

$$H_1: R_T > R_C \text{ (Group T is superior to Group C in terms of ORR)}$$

## 6.2.3. Analysis for the Secondary Efficacy Endpoints

### 6.2.3.1. Progression-free survival

The analysis of PFS will be performed using the Kaplan-Meier method for the ITT analysis set. The PFS distribution of the 2 treatment arms will be compared using the log-rank test, stratified by the stratification factors at randomization. Medians, Q1, Q3 and the proportion of subjects who are free from disease progression and alive at 6, 12, and 18 months from randomization will be provided along with the corresponding 95% CI. Kaplan-Meier curves will be provided by treatment arm.

In addition, the HR between the 2 treatment arms and its 95% CI will be estimated using the Cox proportional hazards regression model, adjusted for the stratification factors at randomization.

Follow-up time for PFS will be summarized as a continuous variable with descriptive statistics by treatment arm.

- For subjects who are censored from PFS and have discontinued from tumor assessment, duration of PFS follow up = Date of Censoring – randomization date +1
- For the remaining subjects (including subjects with progressive disease [PD] based on RECIST 1.1), duration of PFS follow up = Date of analysis cut-off date – randomization date +1

### 6.2.3.2. Objective Response Rate

The ORR will be compared between the 2 treatment arms using the Cochran-Mantel-Haenszel test adjusted for the stratification factors based on the ITT analysis set. ORR and the corresponding 95% CI based on Clopper-Pearson method of each treatment arm will be presented. The odds ratio comparing the 2 treatment arms adjusted for the stratification factors will be presented along with 95% CI. The 2-sided 95% CI of difference for ORR between the treatment and placebo will be calculated based on stratum-adjusted CMH proportion {Koch 1989}.

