### 4.2. Inclusion Criteria

Subjects must meet all of the following inclusion criteria to be eligible for participation in this study.

- 1) Male or female  $\geq 18$  years of age
- 2) Histologically confirmed adenocarcinoma of the stomach or GEJ with inoperable, locally advanced or metastatic disease, not amenable to curative therapy

Adenocarcinoma of the GEJ is defined as tumors that have their center within 5 cm proximal and distal of the anatomical esophagogastric junction as described in Siewert's classification system

- 3) Eastern Cooperative Oncology Group (ECOG)  $\leq 1$
- 4) Measurable disease or non-measurable but evaluable disease, according to RECIST v1.1. Subjects with peritoneal disease would generally be regarded as having evaluable disease and allowed to enter the trial
- 5) Subjects not receiving anticoagulant medication must have an international normalized ratio (INR)  $\leq 1.5$  and activated partial thromboplastin time (aPTT)  $\leq 1.5$  X upper limit of normal (ULN)

The use of full-dose oral or parenteral anticoagulants is permitted as long as the INR or aPTT is within therapeutic limits (according to the medical standard in the institution) and the subject has been on stable dose of anticoagulants for at least 1 week at the time of randomization.

- 6) Adequate hematologic function:
  - a) neutrophils  $\geq 2.0 \times 10^9/L$
  - b) platelets  $\geq 100 \times 10^9/L$
  - c) hemoglobin  $\geq 9$  g/dL

- 7) Adequate hepatic function:
  - a) Direct or total bilirubin  $\leq 1.5 \times$  ULN.
  - b) ALT and AST  $\leq 2.5 \times$  ULN, in case of liver metastases  $\leq 5 \times$  ULN
- 8) Creatinine clearance ( $CL_{cr}$ ) should be  $\geq 30$  mL/min based on the Cockcroft -Gault formula. Subjects with a  $CL_{cr}$  just below 30 mL/min may be eligible if a measured  $CL_{cr}$  (based on 24 hour urine collection or other reliable method) is  $\geq 30$  mL/min
- 9) For female subjects of childbearing potential, willingness to use a protocol-recommended method of contraception from the screening visit throughout the study treatment period, for 90 days following the last dose of study drug (GS-5745/placebo), and for 4 months after the last dose of oxaliplatin or 6 months after the last dose of 5-FU whichever occurs later unless the subject chooses continuous heterosexual abstinence as a lifestyle-choice (see [Appendix 3](#) for more information)

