### **8.3. Analysis Conventions**

#### **8.3.1. Analysis Sets**

##### **8.3.1.1. Intent-to-Treat (ITT) Analysis Set**

The ITT analysis set includes data from all randomized subjects. Study drug assignment will be designated according to randomization.

This analysis set will be used in the analyses of subject characteristics, OS, PFS, ORR and DCR. The analysis of OS based on the ITT analysis set will be considered the primary analysis of the study.

Subjects in the ITT analysis set who do not have sufficient baseline or on-study tumor status information to be adequately assessed for response status (ie, those with best overall responses of NE or ND) will be included in the denominators in calculations of response rates and disease control rates.

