**Table 2 – Time point response: patients with non-target disease only.**

Non target lesions	New lesions	Overall response
CR	No	CR
Non CR/non PD	No	Non CR/non PD a
Not all evaluated	No	NE
Unequivocal PD	Yes or No	PD
Any	Yes	PD

CR = complete response, PD = progressive disease, and NE = inevaluable.  
a a 'Non CR/non PD' is preferred over 'stable disease' for non target disease since SD is increasingly used as endpoint for assessment of efficacy in some trials so to assign this category when no lesions can be measured is not advised.

Best response determination in trials where confirmation of complete or partial response IS required: Complete or partial responses may be claimed only if the criteria for each are met

at a subsequent time point as specified in the protocol (generally 4 weeks later). In this circumstance, the best overall response can be interpreted as in Table 3.

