##### 4.9.2. Phase III trials

Response evaluation in phase III trials may be an indicator of the relative anti tumour activity of the treatments evaluated and is almost always a secondary endpoint. Observed differences in response rate may not predict the clinically relevant therapeutic benefit for the population studied. If objective response is selected as a primary endpoint for a phase III study (only in circumstances where a direct relationship between objective tumour response and a clinically relevant therapeutic benefit can be unambiguously demonstrated for the population studied), the same criteria as those applying to phase II trials should be used and all patients entered should have at least one measurable lesion.

In those many cases where response is a secondary endpoint and not all trial patients have measurable disease, the method for reporting overall best response rates must be pre specified in the protocol. In practice, response rate may be reported using either an 'intent to treat' analysis (all randomised patients in the denominator) or an analysis where only the subset of patients with measurable disease at baseline are included. The protocol should clearly specify how response results will be reported, including any subset analyses that are planned.

The original version of RECIST suggested that in phase III trials one could write protocols using a 'relaxed' interpretation of the RECIST guidelines (for example, reducing the number of lesions measured) but this should no longer be done since these revised guidelines have been amended in such a way that it is clear how these criteria should be applied for all trials in which anatomical assessment of tumour response or progression are endpoints.

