## **3.3. Strata and Covariates**

Subjects will be randomly assigned to treatment groups via the interactive web response system (IWRS) in a 1:1 ratio using a stratified randomization schedule. Stratification will be based on the following variables:

- Geographic regions: Latin America vs All Other Countries
- ECOG status: 0 vs 1
- Tumor site: Gastric vs GEJ

If there are discrepancies in stratification factor values between the IWRS and the clinical database, the baseline values recorded in the clinical database will be used for analyses.

Efficacy endpoints will be evaluated using stratification factors as covariates or stratification variables for analyses, as specified in Section 6.

In the situation where there is insufficient information in a stratum (ie, if there are < 6 subjects or there is no informative event in a stratum by combined treatment arms), pooling of the stratum may be considered with the smallest adjacent stratum for stratified analyses; the smallest stratum is defined as that stratum having the fewest number of subjects or the fewest number of events in case the former is a tie and the adjacent stratum is defined as a stratum having 2 factors of the 3 at the same level and the other factor at an adjacent level.

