### 3.4. Examination of Subject Subsets

Primary (OS) and secondary (PFS and ORR) efficacy endpoints will be examined in the following subgroups:

- Stratification factors:
  - Geographic regions: Latin America vs All Other Countries
  - ECOG status: 0 vs 1
  - Tumor site: Gastric vs GEJ
- Extent of Disease
  - Locally Advanced
  - Metastatic

Note that CRF did not collect extent of disease directly and this will be derived as follows. Subjects with disease stage III at screening will be considered “locally advanced” and those with disease stage IV will be considered as “metastatic”.
- Measurability at Baseline
  - Measurable
  - Non-measurable
- Baseline tumor PD-L1 status
  - Positive: PD-L1 expression if Combined Positive Score (CPS)  $\geq 1$ , using PD-L1 immunohistochemistry (IHC) 22C3 pharmDx assay per its label.
  - Negative: PD-L1 expression if CPS  $< 1$ , using PD-L1 IHC 22C3 pharmDx assay per its label.

Note that inevaluable samples will be considered as missing and excluded from the subgroup analysis.

- Age group
  - < 65
  - $\geq$  65
- Gender
  - Male
  - Female
- Race
  - White
  - Non-White

Adverse events (AEs) and lab abnormalities will be examined in the following subgroups:

- Age group
  - < 65
  - $\geq$  65
- Gender
  - Male
  - Female
- Race
  - White
  - Non-White

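### The ORR test is valid but leaves out baseline measurability, a strong predictor of response that is already collected; adding it would raise ORR power by about 1 to 8 points

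*SAP*

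**What the plan says.** - **Test.** SAP 6.2.3.2: "The ORR will be compared between the 2 treatment arms using the Cochran-Mantel-Haenszel test adjusted for the stratification factors", on the ITT set. SAP 3.3 lists three factors (region, ECOG status, tumor site), which give 8 strata. The odds ratio and the stratum-adjusted difference use the same factors.
- **Eligibility.** Protocol 4.2, criterion 4, admits "Measurable disease or non-measurable but evaluable disease, according to RECIST v1.1", and adds that peritoneal disease will generally count as evaluable.
- **Possible responses.** In Protocol Appendix 7, RECIST Table 2 covers "patients with non-target disease only". Its outcomes are CR, Non-CR/Non-PD, NE and PD. There is no PR row.
- **Denominator.** ORR is CR plus PR in all randomized subjects. Those who cannot be adequately assessed "will be included in the denominators in calculations of response rates and disease control rates" (Protocol 8.3.1.1), and SAP 6.2.1.2 says that they "will be considered as non-responders and will be included in the denominators in calculations of response rates".
- **Measurability.** SAP 3.4 lists "Measurability at Baseline" as a subgroup for OS, PFS and ORR. The protocol synopsis has lesions measured and characterized before randomization.
- **Alpha.** ORR is tested at one-sided 0.016, and only if OS and then PFS have been rejected (SAP 2.1, 2.2, 3.5). No power is stated for ORR.

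**The concern.** A subject with only non-measurable disease can count as a responder only through a complete response, so the chance of response differs sharply between the two measurability groups whatever the treatment. A test that ignores this carries the between-group difference as noise. The noise lowers power, and a chance imbalance in measurability between the arms feeds straight into the ORR comparison. These are two views of the same excess variance, not two separate harms.

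At stake is some power for the third-ranked confirmatory endpoint. Type I error is not affected, and no stated ORR power is contradicted because none is given.

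**Working it through.** **The plan's own figures.** There is no ORR figure to reproduce. The OS and PFS powers that gate ORR do reproduce. With bounds 2.509 and 1.993 at 191 and 286 events, OS one-sided alpha is 0.02499 and power at HR 0.70 is 85.0%. PFS with 322 events, HR 0.70 and one-sided 0.016 has 85.4% power (stated: 85%).

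**Inputs**
- 215 per arm, one-sided 0.016 (z = 2.144): SAP 1.3 and 2.2.
- Control response 40%: Protocol 1.4, stated for measurable disease.
- Experimental response 58%: Protocol 1.4, from 33 evaluable subjects whose measurability is not given. It is assumed here to apply to measurable disease.
- Non-measurable share f: not in the documents, assumed 5% to 25%.
- Response in non-measurable disease: assumed 0%, with 5% CR as a variation.

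**Closed form at f = 20%.** ITT rates are 0.8 x 58% = 46.4% and 0.8 x 40% = 32.0%, a difference of 14.4 points.

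- *Current test.* Pooled rate 0.392.
  - Null SE = sqrt(2 x 0.392 x 0.608 / 215) = 0.0471.
  - SE under the alternative = sqrt((0.32 x 0.68 + 0.464 x 0.536) / 215) = 0.0466.
  - Power = Φ((0.144 − 2.144 x 0.0471) / 0.0466) = 82.2%.
- *Stratified by measurability.* Only the measurable 80% contribute variance, with pooled rate 0.49.
  - Null SE = sqrt(2 x 0.8 x 0.49 x 0.51 / 215) = 0.0431.
  - SE under the alternative = sqrt(0.8 x (0.4 x 0.6 + 0.58 x 0.42) / 215) = 0.0424.
  - Power = Φ((0.144 − 2.144 x 0.0431) / 0.0424) = 88.8%.
- *Null variance ratio.* 0.8 x 0.2499 / 0.2383 = 0.839, so about 16% of the variance is removed.

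**Simulation.** CMH test, 430 subjects, 1:1 within the 8 randomization strata (assumed mix: ECOG 1 55%, Latin America 15%, GEJ 30%), 200,000 replicates. The adjusted test uses the 8 strata for measurable disease plus one non-measurable stratum; 16 unpooled strata give the same result. Matching n is the number per arm at which the current test would reach the adjusted power.

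| Share | Current | Adjusted | Gain (points) | Matching n per arm | Gain x 0.85 x 0.85 |
|---|---|---|---|---|---|
| 5% | 92.1% | 93.5% | 1.4 | 226 | 1.0 |
| 10% | 89.3% | 92.0% | 2.7 | 237 | 2.0 |
| 20% | 82.3% | 88.6% | 6.3 | 258 | 4.6 |
| 25% | 78.1% | 86.4% | 8.4 | 268 | 6.0 |

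The last column allows for the gate, treating ORR as independent of OS and PFS at 85% power each (0.85 x 0.85 = 0.7225). With assumed positive correlations (OS–PFS 0.5–0.7, OS–ORR 0.2–0.4, PFS–ORR 0.4–0.6) the gated gains fall to about 0.7–0.8, 1.4–1.7, 3.8–4.1 and 5.3–5.5 points.

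**Variations at a 20% share**
- 54% versus 40%: 60.1% to 67.6%.
- 50% versus 40%: 33.9% to 38.8%.
- 58% versus 40% with 5% CR in non-measurable disease: 81.9% to 87.0%.

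**Type I error** (1,000,000 replicates, nominal 0.016): 0.0159–0.0160 now, 0.0158–0.0160 with measurability.

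**Pooling.** SAP 3.3 acts on strata with fewer than 6 subjects or no informative event, which would catch non-measurable strata without a responder. On the same 10,000 replicates at a 20% share:

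| Version | Power |
|---|---|
| Current test | 82.9% |
| 8+1 strata | 89.1% |
| Smallest-adjacent pooling, adjacency widened to 3 of 4 factors | 87.8–88.0% |
| Smallest-adjacent pooling, adjacency read literally as 2 of 3 factors | 86.7–87.0% |

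Over all shares, roughly 60% to 90% of the gain survives without a specific pooling rule. With no non-measurable responders, all of it is lost only if those strata are merged into their measurable counterparts (82.3%).

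**The case against.** The plan contains no error. Analyzing by the randomization strata is conventional and matches the OS and PFS analyses. The RECIST text in Appendix 7 (4.9.2) names "all randomised patients in the denominator" as one acceptable way to report response. ORR by measurability will be reported anyway under SAP 3.4. The lists of sensitivity analyses are not visible, so a measurable-disease analysis may already be planned. All of this stands. None of it changes the confirmatory test, which is the only thing at issue.

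The size rests on assumptions. The share is unknown, the 58% is of uncertain relevance, and the largest gains need the upper half of the assumed range. At a 5% share the gain is 1.4 points for ORR alone and 1 point or less after the gate. That also stands, as does the point that assuming independence overstates the gated gain somewhat.

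Adjustment has an interpretive cost. If no non-measurable subject responds, that stratum adds nothing to the statistic, and the test becomes numerically one of measurable disease. The common odds ratio moves accordingly: at a 20% share from (0.464/0.536)/(0.320/0.680) = 1.84 to (0.58/0.42)/(0.40/0.60) = 2.07. The ITT difference stays at 14.4 points. This is a real change in a reported measure and should be stated openly. It does not bias the test.

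Finally, SAP 3.8.1 lets a screening assessment made after randomization but before first dose count as baseline in rare cases, so measurability is not always fixed at randomization. In a blinded trial the effect is small, but the rule should be written down.

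**Conclusion.** The point holds as an efficiency matter. The ORR test is valid, and its denominator is acceptable. It omits a baseline variable that strongly predicts response and is already planned for use elsewhere in the SAP. Under 58% versus 40% in measurable disease and no response otherwise, using it gains about 1.4, 2.7, 6.3 and 8.4 points of ORR power at non-measurable shares of 5%, 10%, 20% and 25%. After the OS and PFS gate the gain is about 0.7 to 6 points, depending on the share and on the correlation between endpoints. The gain was positive in every case examined and is minor if few non-measurable subjects were enrolled. Confidence in the size is medium because the share is not in the documents. The change is worth making but optional.

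**What to change.** Amend SAP 6.2.3.2 before unblinding. SAP 2.4 already records one analysis, the PD-L1 subgroups, added before unblinding.

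1. Keep the ITT denominator.
2. Add baseline measurability (measurable or non-measurable) to the strata for the ORR CMH test, the common odds ratio and the stratum-adjusted difference.
3. For this analysis, pool sparse strata only within a measurability level, for example 8 measurable strata plus one non-measurable stratum. A specific rule is needed because SAP 3.3 defines adjacency for three factors only. SAP 3.3 also makes pooling optional ("pooling of the stratum may be considered with the smallest adjacent stratum for stratified analyses"), whereas Protocol 8.4.1 makes it mandatory.
4. State which assessment defines measurability when screening imaging falls after randomization, and where subjects with no baseline tumor assessment are placed.
5. Keep the present 8-stratum CMH test as a sensitivity analysis.

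The cost is a few sentences and no new data. Three consequences should be stated in the SAP: the odds ratio becomes in effect that of measurable disease; a stratum with no responders counts only in the reported ITT rates, as does any subject without a baseline assessment who is placed in it; and the ORR strata will differ from those for OS and PFS.
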